2.3. Statistical Hypotheses

There are no formal statistical hypotheses for the primary safety endpoints in the study. The main purpose of this study is to provide an evaluation of the difference in the rates of all-cause mortality and all prespecified AESI between the belimumab and placebo groups with a 2-sided 95% CI. SAEs will be summarized descriptively only. See Section [11.1.2](#) for details of the protocol-defined AESIs.

3. STUDY DESIGN

This is a global, multi-center, randomized, double-blind, placebo-controlled, 52-week study to assess mortality and AESI in adults with active, autoantibody-positive SLE treated with belimumab plus standard therapy vs placebo plus standard therapy. Approximately 4,000 subjects will be randomized (1:1) to belimumab plus standard therapy or placebo plus standard therapy. Randomization will be stratified for region (US/Canada vs Central America/South America/Mexico vs Europe/Australia/Israel vs Asia; see [Appendix 1: Countries by Region](#) for details of countries and regions), Safety of Estrogen in Lupus National Assessment Systemic Lupus Erythematosus Disease Activity Index (SELENA SLEDAI) score (≤ 9 vs ≥ 10), and steroid dose (≤ 7.5 mg/day vs >7.5 mg/day prednisone or equivalent). There is no minimum score required for the SELENA SLEDAI to be eligible for this study.

Subjects will receive investigational product (IP) on Days 0, 14, 28, and every 28 days thereafter through Week 48 with a final in clinic visit conducted at Week 52. Subjects who discontinue treatment at any time during the study but do not withdraw from study visits will be followed at 28-day intervals through Week 52. If the subject withdraws from study visits prior to Week 52, an attempt will be made to assess mortality and occurrence of malignancy (including NMSC) at Week 52 and annually for Years 2 through 5. See protocol Section 3.1 for further details. If a subject is not contactable (withdrew consent or lost to follow-up), where allowed by individual subject's legal consent status and individual country regulations, sites may utilize other available records to perform a mortality assessment at Week 52 - this may include search of public records aided by an independent party.

An Independent Data Monitoring Committee (IDMC) will review unblinded safety data until the data are locked and analyzed. The IDMC will monitor all SAEs (including all-cause mortality), serious infections, opportunistic infections and other infections of interest, malignancies (including NMSC), selected serious psychiatric events, suicidality and serious infusion and hypersensitivity reactions. Details of the summaries provided to the IDMC by an Independent Statistical Data Analysis Center (SDAC) are described in the IDMC Charter and IDMC Report Template.

4. PLANNED ANALYSES

4.1. Interim Analyses

The EMA requested that an interim analysis be carried out for monitoring patients' safety.

An interim analysis was planned to be conducted when at least 2,000 randomized subjects had completed through Week 52. The database was released when individual subject records for all subject visits that occurred within the timeframe of the Week 52 visit of the 2,000th subject had been locked. Therefore, the interim analysis also included data for subjects who were randomized but had not yet completed Week 52.

The interim analysis was solely for monitoring patients' safety and reporting event rates to health authorities. It was descriptive in nature and no comparative statistical inferences for claims were to be made.

To minimize bias and maintain data integrity the interim analysis was performed by Statistics Collaborative Inc (SCI), an independent SDAC. They prepared the interim summaries and generated the interim report for IDMC review, producing the same summaries as those created for bi-annual IDMC reviews.

This interim analysis was conducted as planned and submitted to EMA in December 2016.

Following the final analysis of the treatment period through Week 52 as described in Section 4.2, interim summaries will be generated to report post-treatment follow-up mortality and malignancy rates at the end of Year 2, Year 3, and Year 4 for reporting to health authorities.

4.2. Final Analysis

There will be two database releases corresponding to the end of the following study periods as described in Section 9.1.1 and Section 9.1.2:

- Treatment Period (through Week 52)
- Post-Treatment Follow-Up (Years 2 to 5)

The first database release will occur after data through the Week 52 visit (occurring approximately 4 weeks after the last dose of study agent) for all subjects have been collected, verified and validated. Data for subjects who withdraw from IP but stay in the study through Week 52 will be included in this database release. This database will include Year 1 survival status and occurrence of malignancy for subjects who withdraw from the study prior to the Week 52 visit and have follow-up mortality and malignancy data at Week 52. Data for the Years 2 to 5 post-treatment follow-up that has been obtained to this point will be included in the first database release but these data will not be fully validated or locked and will not be reported unless otherwise specified.

The second database release will occur after data through the Year 5 survival status and occurrence of malignancy follow-up have been collected, verified and validated.

This RAP details the planned summaries through the Week 52 treatment period. All outputs required for the Treatment Period (through Week 52) will be listed in the Mock Tables, Listings and Figures (TLFs) Shells document. A separate RAP will be produced to document the planned summaries of the post-treatment follow-up for Years 2-5.

5. SAMPLE SIZE CONSIDERATIONS

5.1. Sample Size Assumptions

It was originally planned that a target of 5,000 SLE subjects would be enrolled in this safety study. The sample size was based on the feasibility of enrolling a large number of SLE subjects in a global trial that would provide a reasonable estimate for mortality and other AESI rates. Assuming a common first year mortality rate of 0.68% for both treatment groups, the precision of the 95% CI for the difference between treatment groups is $\pm 0.46\%$.

Following the completion of 2 additional placebo-controlled trials (BEL112341/C1115, BEL113750), revised mortality estimates based on data from all 5 of the completed studies were as follows: 0.504% (6/1,190 for the placebo group) and 0.564% (14/2,484 for the belimumab group) with a delta of 0.060%.

Using a conservative revised mortality rate of 0.564%, the 95% CI for a 4,000-subject sample size with 1:1 randomization was also $\pm 0.46\%$. As a result, given the revised mortality estimate, a sample size of 4,000 subjects would not result in any loss of precision (i.e., the width of the 95% CI remains unchanged). Therefore, agreement was reached with regulatory authorities to reduce the sample size from 5,000 to 4,000 subjects.

All sample size calculations were performed using the Chi-Square Simple Asymptotic Pearson method in Power Analysis and Sample Size software (PASS 2012).

6. ANALYSIS POPULATIONS

Randomized

The Randomized population is defined as all subjects who are randomized. Summaries using the Randomized population will group subjects according to the treatment that a subject was randomized to receive, regardless of the actual treatment received.

Any subject assigned a treatment randomization number by the Interactive Response System (IXRS) system is considered to have been randomized.

One subject was randomized in the IXRS system but was not entered as a randomized subject into the eCRF, since the site had not administered study agent to the subject. It was not possible to subsequently update the randomization number into the eCRF because the site was closed. Therefore the subject cannot be included in the data displays as part of the randomized population. A footnote will be included on relevant tables to indicate this.

Intention-to-Treat (ITT)

The ITT population is defined as all subjects who are randomized and received at least one dose of study agent. The ITT analysis will be performed per the treatment that a

subject was randomized to receive, regardless of the actual treatment received. All efficacy endpoints will be analyzed using the ITT population unless otherwise specified.

As-Treated

The As-Treated population is defined as all subjects who are randomized and received at least one dose of study agent. The As-Treated population will group subjects according to the actual treatment administered to the subject based on the treatment that the subject received most of the time (>50% of the time). Therefore, if a subject received an incorrect treatment at more than half the visits, the As-Treated treatment group assignment will differ from the randomized treatment group assignment. Safety analysis will be performed on the As-Treated population.

Note: Two investigative sites (PPD and PPD) were investigated for potential GCP non-compliance. These sites were closed during the conduct of the study. The data from both these sites will be included in all analyses/summaries since the primary endpoint and several of the secondary endpoints relate to safety and there were no concerns noted with the AE data. Also, in view of the large total sample size, inclusion of data from these sites (N=14 and N=4 at PPD and PPD in the As Treated population, respectively) is not considered to impact the overall study conclusions.

6.1. Analysis Datasets

All safety summaries will use the observed data, which are the data collected or observed for the subject with no imputation for missing data. Summaries may also include data as adjudicated by the safety review team (SRT) and/or clinical team where specified (see Section 9.2 and Section 9.3 for detail). See Section 9.5.16 for imputation rules for steroid reduction.

7. TREATMENT COMPARISONS

The difference in the rates of all protocol-defined AESI and all-cause mortality, between the belimumab and the placebo groups will be evaluated with a 2-sided 95% CI.

7.1. Data Display Treatment and Other Subgroup Descriptors

The following treatment descriptors will be used on all data tabulations:

- Placebo
- Belimumab 10 mg/kg

For tables presenting baseline demographics and characteristics described in Section 10, the data will also be presented for all subjects using a Total column. Other subgroup descriptors will be described in more detail in Section 8.3.

8. GENERAL CONSIDERATIONS FOR DATA ANALYSES

- All data summaries and analyses will be performed using the latest available version of SAS software (as available at GSK).
- Data displays will follow the shells outlined in the Mock TLFs document which will follow the Benlysta program standards and, as far as possible, follow the agreements proposed by the GSK Integrated Data Standards Library (IDSL).
- The most current version of MedDRA at the time of DBF will be used for reporting.
- The most current version of the Benlysta PSAP at the time of DBF will be used for reporting.
- Where SDTM terminology differs from the eCRF and/or mock shells, the SDTM terminology will be presented in displays unless otherwise specified.

Unless otherwise stated, the following will apply:

- Continuous variables will be summarized with the statistics mean, median, standard deviation (SD), 25th and 75th percentiles, minimum and maximum.
- Categorical variables will be summarized with frequency counts and percentages, or proportions where specified. A 'Missing' category will be added to frequency counts if there is at least one missing record.
- Percentages will be calculated using the number of subjects in the relevant population/treatment group (denoted by N) as the denominator, unless otherwise stated.
- The minimum and maximum will be reported to the same number of decimal places as the raw data recorded in the database.
- The mean, median, 25th percentile and 75th percentile will be reported to one more decimal place than the raw data recorded in the database.
- The SD will be reported to two more decimal places than the raw data recorded in the database.
- A maximum of four decimal places will be used.
- The same rules apply to scores calculated in the derived datasets.
- Percentages will be presented to one decimal place. Incidence rates and difference in incidence rates for the primary analyses will be presented to two decimal places.
- A count of zero will have no corresponding percentage.
- For statistical analyses, all tests will be two-sided and p-values will be presented to a maximum of 4 decimal places.
- Listings will be based on the Randomized population and generally be limited to those required by ICH guidelines and will be sorted by treatment group, investigator number, subject number and visit (where appropriate).

8.1. Multicenter Studies

This is a multicenter trial and subjects will be centrally randomized by region (US/Canada vs Central America/South America/Mexico vs Europe/Australia/Israel vs Asia – See [Appendix 1](#)). There will be no analyses performed at the center level.

Note that in this study, no subjects from Israel were randomized.

8.2. Other Strata and Covariates

In addition to randomization by region, randomization will include stratification by subjects' screening SELENA SLEDAI score (≤ 9 vs. ≥ 10) and steroid dose (≤ 7.5 mg/day vs >7.5 mg/day prednisone or equivalent). Any subgroup summaries (or analyses controlling for stratification factors as covariates, as applicable) will use data from the eCRF, not the strata variable from the randomization dataset.

Differences are anticipated between the randomization strata and the eCRF strata for baseline steroid dose. Sites were instructed to calculate the baseline dose for randomization using all steroids received for any indication (i.e. SLE and non-SLE). However, in the eCRF completion guidelines sites were instructed to record only steroids taken for SLE, pre-infusion (as prophylaxis against infusion reactions and hypersensitivity reaction), for AESI and SAEs in the eCRF. For subgroup summaries and for derivation as covariates (where used for analysis adjustment), only steroids received for SLE will be used to calculate baseline steroid dose. See Section [9.5.16](#) for details.

Other covariates of interest may include age, race, gender, complement levels and anti-dsDNA as defined in Section [8.3](#).

8.3. Examination of Subgroups

Since the reported incidence for primary safety endpoints is expected to be low, subgroup categories may be refined where necessary.

Mortality, AESIs and all AEs (i.e. AESI and SAEs) during the On-Treatment period will be summarized by the following subgroups:

- Age (<65 years vs. ≥ 65 years)
- Gender (Male vs. Female)
- Race Stratification (Black vs. Other). The Black category is defined as subjects who are in the race category “Black or African American”. The race hierarchy rule (Section [9.5.10](#)) will not apply and a subject will be categorized as Black if they have selected multiple race categories and any of them is “Black or African American”.
- Randomization Stratification Factors (see Section [8.2](#), derived from eCRF data):
 - Region (US/Canada, Central America/South America/Mexico, Europe/Australia/Israel, Asia)
 - Screening SELENA SLEDAI (≤ 9 , ≥ 10). Note: if any individual item is missing the total score cannot be calculated, however if the subject can be definitively

categorized as ≤ 9 or ≥ 10 regardless of the response to the missing item(s) then the appropriate subgroup will be assigned.

- Steroid dose (≤ 7.5 mg/day, >7.5 mg/day prednisone or equivalent) (baseline average daily dose, see Section 9.5.16.1). Note: Only systemic steroids given for SLE are included in the derivation.
- Screening Complement Levels and Anti-dsDNA (Low Complement and High Anti-dsDNA binding, Not (Low Complement and High Anti-dsDNA binding)), derived from the screening SELENA SLEDAI assessment. This subgroup is intended to be an indicator of high versus low disease activity. Note: If the evaluations to the SELENA SLEDAI assessment questions “Low Complement” and “Increased DNA Binding” are both missing, the subject will not be classified into one of the subgroup categories. If either item is marked “No”, the subject will be classified into the Not (Low Complement and High Anti-dsDNA binding) group regardless of whether the other item is missing or “Yes”.

Demographic and baseline characteristics and baseline disease activity will also be summarized by all subgroups except Screening Complement Levels and Anti-dsDNA.

8.4. Multiple Comparisons and Multiplicity

There is no statistical hypothesis to be tested (no formal statistical testing) for the primary safety analyses, and therefore no need to control for multiple comparisons. Analyses of the secondary efficacy endpoints will also not be subject to any multiple comparison procedure. All statistical tests will be 2-sided and performed at an overall significance level of 0.05.

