12.1. Major Efficacy Analyses

12.1.1. Percent of Subjects with Prednisone Reduction by $\geq 25\%$ from baseline to ≤ 7.5 mg/day during Week 40 through Week 52

Primary Analysis

For this analysis, only steroids used to treat SLE will be included and only subjects with a baseline average daily prednisone dose >7.5 mg/day will be included. See Section 9.5.16.1 for derivation of baseline prednisone dose and Section 9.5.16.2 for derivation of average prednisone use between Week 40 to Week 52.

The percent of subjects whose average prednisone dose has been reduced by $\geq 25\%$ from baseline to ≤ 7.5 mg/day during Weeks 40 through 52 will be compared between belimumab and placebo using a logistic regression model. Independent variables in the model will include treatment group, baseline prednisone dose, and the following

randomization stratification factors per the eCRF: screening SELENA SLEDAI score (≤ 9 vs. ≥ 10), and region. A responder is defined as having a prednisone reduction by $\geq 25\%$ from baseline to ≤ 7.5 mg/day during Weeks 40 through 52.

Any subject who withdraws from the study or adds new immunomodulatory agents used to treat SLE (note that this will include switches) prior to the Week 52 visit will be considered having no steroid reduction.

A summary of the number and percentage of subjects who are responders by treatment group, the treatment difference versus placebo, the odds ratio and 95% CI versus placebo, and a p-value for the odds ratio will also be provided.

Sensitivity Analysis

- To examine the robustness of the results, a sensitivity analysis of the SLE-related steroid reduction will be performed without considering any information related to the use of new immunomodulatory agents (note that this will include switches).

Additional Summaries of Prednisone

- A summary of the number and percentage of subjects with average SLE-related daily prednisone dose ≤ 7.5 mg/day and > 7.5 mg/day at baseline (Day 1) and treatment completion date will be presented for treatment completers.
- The cumulative SLE-related prednisone dose will be derived as described in Section 9.5.16.3. A table of descriptive statistics will be presented including the mean, standard deviation, median, 25th and 75th percentiles, minimum and maximum.
- A listing of cumulative SLE-related prednisone dose will be displayed by treatment and subject.

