12.2.3. SLICC/ACR Damage Index

SLICC/ACR is attached in [Appendix 5: SLICC/ACR Damage Index](#).

A listing of all available SLICC/ACR data will be provided, including the analysis result for each item, the total score and the change from baseline at Week 52.

12.2.3.1. SLICC/ACR Damage Index Change from Baseline at Week 52

The change from baseline in SLICC/ACR Damage Index score at Week 52 will be summarized for belimumab and placebo.

The table will display the summary statistics for the SLICC/ACR Damage Index score at baseline and at Week 52. The table will also display the mean change from baseline, standard deviation, median, 25th and 75th percentiles, minimum and maximum. Only subjects who complete the full course of study agent through 48 weeks and complete the study to Week 52 will be included in the summary at Week 52.

A separate summary will be produced for subjects who complete the study through 52 weeks, i.e. subjects with off-treatment data will be included. The table will display the summary statistics for the SLICC/ACR Damage Index score at baseline and at Week 52. The table will also display the mean change from baseline, standard deviation, median, 25th and 75th percentiles, minimum and maximum.

12.2.3.2. SLICC/ACR Damage Index Worsening at Week 52

The number and percentage of subjects with worsening in their SLICC/ACR Damage Index score compared with baseline at Week 52 will be presented. Worsening is defined as a change in score (Week 52 visit minus Baseline) >0. The percentage of subjects with

worsening in their SLICC/ACR Damage Index score at Week 52 will be compared between belimumab and placebo using a logistic regression model. The independent variables in the model will include treatment group and randomization strata per the eCRF: steroid dose (≤ 7.5 mg/day vs > 7.5 mg/day prednisone or equivalent used to treat SLE), region, screening SELENA SLEDAI score (≤ 9 vs. ≥ 10), and baseline SLICC/ACR Damage Index score.

The table will display the number and percentage of subjects with worsening in their SLICC/ACR Damage Index score by treatment group, the treatment difference versus placebo, the odds ratio and 95% CI versus placebo, and a p-value for the odds ratio.

Only subjects who complete the full course of study agent through 48 weeks and complete the study to Week 52 with a baseline and post-baseline assessment will be included in the analysis. See Section 9.5.19 for further detail.

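### The Week 52 analysis plan states an overall 0.05 level for all tests just after waiving multiplicity control, while two unadjusted efficacy p-values are planned

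*SAP*

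**What the plan says.** Section 8.4 of the Week 52 RAP makes three statements in sequence.

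- On safety: "There is no statistical hypothesis to be tested (no formal statistical testing) for the primary safety analyses".
- On efficacy: "Analyses of the secondary efficacy endpoints will also not be subject to any multiple comparison procedure".
- On the level: "All statistical tests will be 2-sided and performed at an overall significance level of 0.05".

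Two later sections plan a p-value on efficacy data, each from a logistic regression.

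- Section 12.1.1, steroid reduction (the major efficacy endpoint). The output includes "the odds ratio and 95% CI versus placebo, and a p-value for the odds ratio will also be provided". On the analysis set: "only subjects with a baseline average daily prednisone dose >7.5 mg/day will be included".
- Section 12.2.3.2, SLICC/ACR Damage Index worsening at Week 52. The output includes "the odds ratio and 95% CI versus placebo, and a p-value for the odds ratio". The analysis set begins: "Only subjects who complete the full course of study agent through 48 weeks and complete the study to Week 52", and a baseline and a post-baseline assessment are also required.

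No section divides alpha between the two tests, orders them, or makes one conditional on the other. Section 2.2.3 acknowledges that the protocol does not explicitly list the SLICC/ACR index as an endpoint, and adds analyses of it because it is of interest.

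**The concern.** An overall level of 0.05 across more than one test is a property that some procedure has to deliver. Section 8.4 says that no such procedure applies to efficacy and then states the property anyway. A reader of the study report could cite either sentence.

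The ambiguity matters most for the SLICC/ACR p-value. It belongs to an endpoint that the RAP added, it comes from a set selected after randomization (completers of both treatment and study), and it is tabulated in the same format as the major efficacy endpoint. If steroid reduction were not significant and SLICC/ACR worsening were, the Section 8.4 sentence could be used to present the second result as falling within a 5% overall error rate. The plan provides no such protection.

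**Working it through.** **Inputs**

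- Level per test: 0.05, two-sided (Week 52 RAP, Section 8.4). No reduced level appears in Sections 12.1.1 or 12.2.3.2.
- Number of explicit efficacy p-values: two (Sections 12.1.1 and 12.2.3.2).
- Safety analyses: estimation only, so no tests are added (Sections 2.3 and 8.4).
- Interim analysis: descriptive, with no comparative inference and no Type I adjustment (protocol Section 8.1; RAP Section 4.1), so no tests are added.
- Correlation ρ between the two test statistics under the null: not given. Assumed to be 0 to 0.5; the range up to 1 is also shown.

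**Step 1: when is the stated 0.05 correct?** With one test, 1 − 0.95 = 0.05. With two tests, it is correct only in the limit ρ = 1. That limit is not realistic here, because the outcomes differ and the analysis sets overlap only in part.

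**Step 2: two tests at 0.05, both nulls true.**

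- Independent: 1 − 0.95² = 1 − 0.9025 = 0.0975.
- Upper bound under any dependence (Bonferroni): 0.05 + 0.05 = 0.10.

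**Step 3: correlated tests.** With (Z₁, Z₂) bivariate normal with correlation ρ, the error is 1 − P(|Z₁| ≤ 1.96 and |Z₂| ≤ 1.96).

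| ρ (assumed) | Chance of at least one false positive |
|---|---|
| 0 | 9.75% |
| 0.2 | 9.64% |
| 0.3 | 9.51% |
| 0.5 | 9.07% |
| 0.7 | 8.35% |
| 0.9 | 7.04% |
| 1 (limit) | 5% |

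**Step 4: only one null true.** If belimumab really does reduce steroid use, only the SLICC/ACR null can be falsely rejected, and the chance of that is 5%. The figures in Steps 2 and 3 therefore apply only when neither endpoint has an effect.

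**Step 5: the steroid sensitivity analysis.** Section 12.1.1 adds that "a sensitivity analysis of the SLE-related steroid reduction will be performed without considering any information related to the use of new immunomodulatory agents". It names no p-value for this analysis, so it is not counted above. If it were read as a third test, the error would be about 11-13%, assuming correlations of 0.7 to 0.9 with the main steroid test and 0 to 0.3 between the SLICC/ACR test and each of the steroid tests. The bound would be 3 × 0.05 = 15%.

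**The case against.** The strongest reply is that the plan never promises family-wise control. The sentence just before the 0.05 statement waives it openly, so the natural reading is that 0.05 is the default level for each test. The rest of the plan fits that reading. Efficacy is described as secondary in nature, there is a single major efficacy endpoint, SLICC/ACR is placed under other efficacy analyses (Section 12.2), and no efficacy claim based on it is planned. Waiving multiplicity control for secondary efficacy in a safety study is acceptable.

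Much of this stands, and it is why the point is small. It does not rescue the word *overall*. If a per-test level is meant, the word is wrong, and it appears in the section whose subject is multiplicity.

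A second reply is that *overall* refers to the interim and final looks together. The interim analysis was descriptive and used no alpha, so on that reading the word has nothing to do.

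A reader might also infer more than the documents support:

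- That the trial's efficacy error rate simply is 9-10%. That figure needs both nulls to be true and a correlation of about 0.5 or less, which the documents do not supply.
- That the mortality or adverse-event results are compromised. They are confidence-interval estimates and do not depend on this sentence.
- That a fixed testing order, steroid reduction and then SLICC/ACR worsening, is the right remedy. It would make the stated 0.05 true, but it would give confirmatory standing to a completers-only analysis of something not explicitly a protocol endpoint whenever steroid reduction succeeded.

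**Conclusion.** The concern holds as a minor one. Section 8.4 states a property, an overall 0.05 level, that the plan lacks, and its own preceding sentence contradicts it. Across the two planned efficacy p-values, the chance of at least one false positive is at most 10% if both nulls are true. It is about 9-10% if, in addition, the test statistics have a correlation between 0 and 0.5 (an assumption). It falls towards 5% only as the correlation approaches 1.

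The waiver is disclosed and the analyses themselves need not change. What needs correcting is the statement about error control and the undefined standing of the SLICC/ACR p-value.

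**What to change.** In Section 8.4, replace the reference to an overall significance level of 0.05 with: *a per-test (nominal) two-sided 0.05 level, with no control of the overall error across efficacy endpoints*. Add one sentence naming steroid reduction as the only efficacy test that can be interpreted at 5%, and labelling the completers-only SLICC/ACR worsening p-value nominal and exploratory. Use the same labels in the study report.

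The cost is about two sentences and no reanalysis. The downside is small: no overall 5% claim can be made for efficacy, and SLICC/ACR worsening cannot be claimed as confirmatory.

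Timing also favours this wording. The Week 52 RAP was finalized on 18 October 2018 and the data were unblinded on 2 January 2019 (Years 2 to 5 RAP, Section 1). A testing order or alpha split added after that date would be post hoc, whereas calling the p-values nominal claims less than the plan does and can still be done.
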